1. OBJECTIVES

Phase I

Primary:

To determine the maximal tolerated dose (MTD) of clofarabine to be used in portion II of the study

Phase II

Primary:

To determine the response rate of the DAC-CIA regimen

Secondary:

- A) To determine the toxicity of the combination regimen
- B) To determine the disease-free survival (DFS) and overall survival (OS) rates

2. RATIONALE

2.1 Acute Myelogenous Leukemia

Acute myelogenous leukemia (AML) is the most common acute leukemia in adults. It is estimated that 13,780 men and women will be diagnosed with and 10,200 men and women will die of acute myeloid leukemia in the year 2012.¹ AML is a disease with a poor prognosis with a 5-year survival of only around 30%.^{2,3} Certain subgroups of AML have a particularly worse

outcome such as patients with relapsed and/or refractory AML and AML arising from antecedent myelodysplastic syndrome (MDS) or myeloproliferative neoplasms (MPNs).

Although most patients with AML will achieve remission with induction chemotherapy; many patients will relapse, despite the administration of post-remission therapies. Relapses may occur weeks to many years later. Up to 10% of patients will be refractory to induction chemotherapy. Both of these groups of patients (relapsed/refractory) constitute a particularly poor risk group. Although an allogeneic stem cell transplant would be considered a recommended approach for most of these patients, it is feasible only in a small number of patients. Many novel drugs and approaches are being investigated for this group of patients. However, the CR rates have been, in general, less than 30%.⁴⁻⁶ The Eastern Cooperative Oncology Group (ECOG) conducted a randomized 3-arm phase II trial where relapsed/refractory AML patients received either intermediate-dose cytarabine/gemtuzumab ozogamicin, or intermediate-dose cytarabine/liposomal daunorubicin, or intermediate-dose cytarabine/ cyclophosphamide/ topotecan.⁴ The CR/CRp (CR with incomplete platelet count recovery) rates achieved were low, ranging from 4% to 12%, depending on the study arm. Cortes et al. performed an exploratory study in relapsed/refractory AML patients combining p53 antisense oligonucleotide Cenersen with idarubicin either alone or with cytarabine.⁵ Ten of the 53 (19%) patients achieved CR/CRp. These data highlight the need for development of better treatment strategies for this group of patients.

AML arising from antecedent MDS/MPN: In a recent study by Bello and colleagues, outcomes of patients who progressed from MDS were studied.⁷ In the subgroup of patients who had failed hypomethylating agents (the current FDA approved standard therapy for MDS), the median overall survival (OS) was only 3.7 months from the time of AML diagnosis. Those with poor

2.2 Combination chemotherapy for AML: Emerging role of purine analogs

Anthracyclines have been traditionally combined with cytarabine in AML. Two recent publications highlighted higher response rates and better disease-free survival in both younger and older patients with frontline AML when high-dose daunorubicin (90 mg/m²/dose) was used in a “7+3” induction combination highlighting the activity of this class of agents for AML therapy.^{8,9} Pautas et al randomized 468 AML patients ages 50 to 70 years to 3 induction anthracycline regimens: idarubicin 12 mg/m² daily for 3 days, idarubicin 12 mg/m² daily for 4 days, and high-dose daunorubicin 80 mg/m² daily for 3 days.¹⁰ The CR rate with idarubicin daily for 3 days was higher than with high-dose daunorubicin (83% vs. 70%). A recent report from the Polish Acute Leukemia Group provides evidence for adding purine analog cladribine to the standard daunorubicin plus cytarabine regimen.¹¹ In a phase III study, 652 untreated patients (ages 18 to 60 years) with AML were randomized to receive either daunorubicin plus cytarabine (DA), or DA plus fludarabine, or DA plus cladribine. The CR rate was significantly higher in the cladribine arm compared to the DA arm (67.5% vs. 56%; p=0.01). The OS was also better in the cladribine arm compared to DA arm (3-year OS: 45% vs. 33%, p=0.02). The survival advantage of the cladribine arm over the DA arm was observed among patients age 50 years or older (p=0.005), those with initial leukocyte count above 50 x 10⁹/L (p=0.03), and those with unfavorable karyotype (p=0.03).

2.3 Clofarabine in AML

Clofarabine (2-chloro-20-fluoro-deoxy-9-b-D-arabinofuranosyladenosine) is a second-generation nucleoside analog, which was developed as a hybrid molecule to combine the most favorable pharmacokinetic properties of both fludarabine and cladribine and has better stability with higher affinity to deoxycytidine kinase, the rate-limiting step in phosphorylation of nucleosides.¹²

Clofarabine acts as an inhibitor of both DNA synthesis and the enzyme ribonucleotide reductase (RNR). Its structural characteristics render it resistant to deamination by adenosine deaminase and phosphorolytic cleavage by bacterial purine nucleoside phosphorylase.¹³⁻¹⁶ Single agent clofarabine has demonstrated activity in phase I-II studies in AML.^{17,18} As a potent inhibitor of ribonucleotide reductase (RNR) and by means of biochemical modulation, clofarabine is more ideally suited to be incorporated into combinations such as have been tested and validated with cytarabine in AML.¹⁹ We have previously conducted a study combining cytarabine with clofarabine in patients with relapsed/refractory AML.²⁰ At doses of 1 g/m2 daily x 5 days for cytarabine and 40 mg/m2 daily x 5 days for clofarabine, we reported a response rate of 40% (28% complete remission) in 29 patients with a median age of 59 years (18 to 84 years).

Responses extended to patients with primary refractory disease and those with abnormal cytogenetics. Other groups have since followed this lead and published comparable results.²¹ We have also reported adaptively randomized study of lower-dose clofarabine (30mg/m2 IV daily for 5 days) with or without low-dose cytarabine (20mg/m2 SQ daily for 14 days) in previously untreated older (≥ 60 years) with AML. CR rate was significantly higher with the combination therapy (63% vs. 31%; $p=0.025$). The combination arm also had improved event free survival (7.1 months vs. 1.7 months; $p=0.04$), but not overall survival (11.4 months vs. 5.8 months; $p=0.1$). No excess toxicity was observed in the combination arm. We have previously explored

the combination of clofarabine with cytarabine and anthracycline (CIA regimen). In a phase I study for patients with relapsed/refractory AML, the following doses were established for further evaluation: clofarabine 22.5 mg/m² daily x 5 days, idarubicin 6 mg/m² daily x 3 days, and cytarabine 0.75 mg/m² daily x 5 days.²² In a recent update of a phase II study of 63 patients treated with CIA regimen,²³ the overall response rate was 38% including 21% CR. Median overall survival was 34 weeks for all patients and 66 weeks for those patients who achieved CR/CRp. Twenty-four patients (38%) were able to proceed with a stem cell transplant. Induction mortality was at 8%. Toxicities were manageable.

2.4 The role of Hypomethylating agents in AML

In the last decade there has been an increasing recognition of the important pathogenetic role of epigenetic changes in leukemogenesis.²⁴ Aberrant DNA methylation of tumor suppressor genes, leading to their inactivation is an important step in carcinogenesis.²⁵ Thus, drugs such as DNA methyltransferase inhibitors which lead to DNA hypomethylation may lead to reexpression of tumor suppressor genes. Two such agents, 5-azacytidine and decitabine are currently approved by the United States Food and Drug Administration for the treatment of MDS and have demonstrated single-agent activity in AML patients.²⁶⁻²⁹

Kantarjian et al. performed a multicenter, randomized, open-label, phase III trial comparing the efficacy and safety of decitabine with treatment choice (TC, supportive care or cytarabine 20 mg/m² per day subcutaneously for 10 consecutive days every 4 weeks) in older patients (age \geq 65 years) with newly diagnosed AML and poor- or intermediate-risk cytogenetics.²⁶ Patients (n=485) were randomly assigned 1:1 to receive decitabine 20 mg/m² per day as a 1-hour intravenous infusion for five consecutive days every 4 weeks or TC. The primary analysis

showed a nonsignificant increase in median OS with decitabine (7.7 months; 95% CI, 6.2 to 9.2) versus TC (5.0 months; 95% CI, 4.3 to 6.3; $p=0.108$). Based on this trial results, on September 28, 2012, the European Commission approved decitabine for the treatment of adult patients (age 65 years and above) with newly diagnosed AML, who are not candidates for standard induction chemotherapy.

2.5 Combination of hypomethylating agents and chemotherapy in AML

There is preclinical evidence that DNA hypomethylating agents can sensitize tumor cells to cytotoxic chemotherapy.³⁰⁻³⁴ Studies in the late 1970's showed that combination of 5-azacytidine and cytarabine was synergistic both in vitro and in vivo, when used sequentially whereas concurrent administration was antagonistic.³⁵ These studies were, however, done using higher doses of 5-azacytidine (600-1500 mg/m² per course), which led to significant non-hematologic toxicities in these earlier clinical trials.³⁶ It is now known that the effects of 5-azacytidine and decitabine on DNA hypomethylation occur at a significantly lower dose range; and the standard dose of decitabine is 20mg/m² daily for 5 days.³⁷⁻⁴⁰ Qin et al. reported the synergism of decitabine at clinically relevant doses with cytarabine in the HL-60 AML cell line.³⁴ The authors showed that hypomethylated cells following treatment with decitabine were more likely to undergo apoptosis when treated with cytarabine. Scandura et al. recently reported outcomes of 30 untreated younger (≤ 60 years old) patients with intermediate/poor risk AML who received decitabine as a 'priming' agent prior to the conventional '7+3' chemotherapy.⁴¹ Overall CR rate of 83% was noted (57% with first induction). No excess toxicity was noted with the decitabine priming approach and the toxicity profile was similar to the standard induction. Though there was a prior concern for potential prolonged myelosuppression with this approach, the authors, on

the contrary found faster platelet recovery (median 22 days) with the decitabine ‘priming’ compared to their prior experience with cytarabine-containing induction regimens.⁴¹ The German group has reported preliminary results of a dose-finding study in which 5-azacytidine was used at 2 different dosing regimen (75mg/m² and 37.5mg/m²) immediately prior to standard induction with ‘7+3’.⁴² In their preliminary analysis, the tolerability of the 2 arms was similar and they have selected 75mg/m² dose (the standard dosing for 5-azacytidine) as the phase II dose.

Based on these observations, we hypothesize that addition of decitabine to our current standard chemotherapy regimen (clofarabine, idarubicin, cytarabine), the DAC-CIA regimen, would be synergistic and would ultimately lead to an improvement in CR rates and patient outcomes. We propose a phase I-II study. The primary endpoint of the phase I study is to determine the maximal tolerated dose (MTD) of clofarabine to be used in the phase II portion of the study. The primary endpoint of the phase II study is to determine the response rate of DAC-CIA regimen.

2.6 Acute Lymphoblastic Leukemia (ALL)

Patients with relapsed/Refractory ALL constitute a poor risk group with dismal long-term outcomes. Fielding and colleagues analyzed the outcomes of 609 relapsed adult ALL patients who were treated on the MRC trial.⁴³ The median OS was only 5.5 months with the 5-year OS of only 7%. Similar poor outcomes of relapsed patients with ALL have been reported by the French and PETHEMA groups.^{44,45} Thus, patients with relapsed ALL continue to be a challenging subgroup of patient and novel treatment strategies are indicated.

Epigenetic dysregulation is now thought to play an important role in pathogenesis of ALL.⁴⁶ Promoter hypermethylation of cancer related genes such as Wnt, Src and others have been shown

to be an independent prognostic marker for poor survival in ALL patients.⁴⁷⁻⁴⁹ Preclinical evidence supports use of hypomethylating agents such as decitabine in ALL patients.^{46,50} In the proposed clinical trial, all the chemotherapy drugs (clofarabine, idarubicin, cytarabine) have been shown to have independent anti-leukemic activity in ALL.^{17,51,52} Therefore, the proposed regimen (decitabine followed by the CIA chemotherapy) deserves evaluation as a treatment strategy for relapsed/refractory ALL patients. We plan to enroll ALL patients only in the phase II part of the study.

3. BACKGROUND DRUG INFORMATION

3.1. Idarubicin:

Idarubicin is commercially available.

Mechanism of action:

Similar to doxorubicin and daunorubicin; inhibition of DNA and RNA synthesis by intercalation between DNA base pairs

Adverse effects:

- Cardiovascular: Transient EKG abnormalities (supraventricular tachycardia, S-T wave changes, atrial or ventricular extrasystoles); generally asymptomatic and self-limiting. Congestive heart failure, dose-related. The relative cardiotoxicity of idarubicin compared to doxorubicin is unclear. Some investigators report no increase in cardiac toxicity at cumulative oral idarubicin doses up to 540 mg/m²; other reports suggest a maximum cumulative intravenous dose of 150 mg/m².
- Central nervous system: Headache
- Dermatologic: Alopecia (25% to 30%), radiation recall, skin rash (11%), urticaria

- Gastrointestinal: Nausea, vomiting (30% to 60%); diarrhea (9% to 22%); stomatitis (11%); GI hemorrhage (30%)
- Genitourinary: Discoloration of urine (darker yellow)

3.2. Cytarabine

Cytarabine is commercially available.

Mechanism of action:

Cytarabine is an antimetabolite. Cytarabine is cell cycle-specific for the S phase of cell division. Activity occurs as the result of activation to cytarabine triphosphate in the tissues and includes inhibition of DNA polymerase and incorporation of cytarabine into DNA and RNA.

Adverse effects:

COMMON

- Cardiovascular: Thrombophlebitis
- Dermatologic: Rash, conjunctivitis
- Endocrine metabolic: Hyperuricemia
- Gastrointestinal: Anal inflammation, Diarrhea, Loss of appetite, Nausea, Stomatitis, Ulcer of anus, Ulcer of mouth, Vomiting
- Hematologic: Decreased reticulocyte count, Megaloblastic anemia
- Hepatic: Decreased liver function
- Other: Fever

SERIOUS

- Hematologic: Anemia, Bleeding, Leukopenia, Thrombocytopenia
- Immunologic: Anaphylaxis

- Neurologic: Neuropathy
- Renal: Kidney disease
- Other: Infectious disease, Sepsis

3.3. Clofarabine

Clofarabine is commercially available.

Mechanism of action:

Clofarabine potently inhibits DNA synthesis by inhibiting both DNA polymerase and ribonucleotide reductase. Clofarabine demonstrated the ability to disrupt mitochondrial integrity that results in the release of pro-apoptotic proteins, cytochrome C and apoptosis-inducing factor.

Adverse effects:

- Hematologic: Myelosuppression, infections
- Hepato and Gastrointestinal: Nausea/vomiting, diarrhea, mucositis, stomatitis/pharyngitis, hyperbilirubinemia, increase of SGPT and/or SGOT, abdominal pain or cramping, peritonitis, pancreatitis, liver failure
- Dermatologic: Skin rash with blisters (particularly hand-foot syndrome), alopecia, Steven-Johnson's syndrome
- Systemic: Fatigue, asthenia, anorexia, lethargy, malaise, mental status changes/coma, alopecia
- Allergic reactions: fever, muscle aches, edema, dyspnea
- Cardiology: Congestive heart failure
- Nephrology: Kidney failure
- Autoimmune reactions: antiplatelet antibodies, erythema nodosum

3.4. Decitabine

Decitabine is commercially available.

Mechanism of action:

Decitabine is a nucleoside analog. It is metabolized intracellularly by the enzyme deoxycytidine kinase and gets incorporated into DNA. It is believed to exert its antineoplastic effects by causing hypomethylation of DNA and direct cytotoxicity on abnormal hematopoietic cells in the bone marrow. Hypomethylation may restore normal function to genes that are critical for differentiation and inhibition of proliferation.

Adverse effects:

Myelosuppression, nausea/vomiting, diarrhea, mucositis, skin rash, fatigue, mental status changes/coma, allergic reactions (including fever, muscle aches, edema, dyspnea), congestive heart failure, liver failure, kidney failure, infections, lethargy, malaise, asthenia, alopecia, peritonitis, anorexia, stomatitis/pharyngitis, hyperbilirubinemia, increase of SGPT and/or SGOT, abdominal pain or cramping.

Also reported on decitabine trials, but with the relationship to decitabine still undetermined: allergic reaction, allergic rhinitis, GVHD, atrial fibrillation, cardiac ischemia/infarction, cardiopulmonary arrest, hypotension, left ventricular systolic dysfunction, right ventricular dysfunction, fever, insomnia, rigors/chills, weight loss, pruritus, rash, anal ulcer, ascites, constipation, abdominal distention, esophagitis, GI obstruction, ileus, taste alteration, CNS hemorrhage, GI hemorrhage, lung hemorrhage, nose hemorrhage, petechiae, urinary hemorrhage, cholecystitis, liver failure, infection without neutropenia, opportunistic infection, perianal abscess, head/neck edema, alkaline phosphatase, creatinine, hypercalcemia, hyponatremia,

fracture, agitation, CNS ischemia, confusion, depression, dizziness, extrapyramidal/involuntary movement, motor neuropathy, psychosis, seizure, sensory neuropathy, bone pain, headache, muscle pain, urinary pain, ARDS, bronchospasm, cough, dyspnea, hiccups, pneumonitis/pulmonary infiltrates, cystitis.

4. ELIGIBILITY CRITERIA

Inclusion criteria:

- Sign an IRB-approved informed consent document.
- Age ≥ 18 to 65 years.
- Diagnosis of AML [other than acute promyelocytic leukemia] with refractory/relapsed disease (Patients must be either primary refractory, in relapse 1, or in relapse 2).

NOTE: Patients with AML arising from prior MDS or MPN will be eligible even if they have not received treatment for the AML.

NOTE: Patients with relapsed/refractory ALL will also be eligible for the phase II part of the study.

NOTE: Use of hydroxyurea and/or up to 4 doses of cytarabine, for emergent cytoreduction is allowed

- ECOG performance status of ≤ 2 at study entry.
- Organ function as defined below (unless due to leukemia):
 - Serum creatinine ≤ 3 mg/dL
 - Total bilirubin ≤ 2.5 mg/dL
 - ALT (SGPT) $\leq 3 \times$ ULN or $\leq 5 \times$ ULN if related to disease
- Cardiac ejection fraction $\geq 40\%$ (by either cardiac ECHO or MUGA scan)

- Women of childbearing potential must have a negative serum or urine pregnancy test within 7 days. Men must agree not to father a child and agree to use a condom if his partner is of child bearing potential.

Exclusion Criteria:

- Breast feeding women
- Patients with uncontrolled active infections (viral, bacterial, and fungal are not eligible).
- Patients with active secondary malignancy will not be eligible unless approved by the PI.
- NOTE: Prior therapy with decitabine, clofarabine, idarubicin, or cytarabine is allowed, unless the prior therapy is identical to the schema/schedule proposed in this study

5. TREATMENT PLAN

5.1. Study design

The study will include a phase I portion to determine MTD dose of clofarabine to be used in the subsequent phase II portion. Starting with Dose level 1, the patient will be enrolled by cohort of 3. Once the DLT assessment for the 3 patients is completed, a sequential of another cohort of 3 patients will be enrolled. If at any time, we see more than 30% patients experiencing DLT, we will de-escalate to dose level (-1). The same above monitoring rule will also be applied to dose level -1. A total of 18 patients will be enrolled. Once the phase II dose of clofarabine is established, additional patients will be enrolled in the phase II portion of the study.

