5.2. Induction

5.2.1 Phase I (fixed dose of decitabine 20mg/m2 days 1-5, idarubicin 10 mg/m2 days 6-8 and cytarabine 1 g/m2 days 6-10)

Clofarabine 15 mg/m2 IV over approximately 1 hour daily.

Dose levels and dose escalation schema are described below.

Dose level	Clofarabine 15 mg/m2/day IV daily
-1	Clofarabine daily for 3 days (days 6-8)
1	Clofarabine daily for 4 days (days 6-9)

Decitabine 20 mg/m2 IV over approximately 1 hour daily for 5 days (days 1-5)

Idarubicin 10 mg/m2 IV over approximately 30 minutes daily for 3 days (days 6-8)

Cytarabine 1 g/m2 IV over approximately 2 hours daily for 5 days (days 6-10)

Idarubicin will follow clofarabine by 1 to 2 hours and cytarabine will follow clofarabine by 3 to 6 hours. All chemotherapeutic agents will be dosed, prepared, and administered according to MDACC institutional guidelines. BSA will be recalculated prior to each subsequent course.

A DLT is defined as a clinically significant adverse event or abnormal laboratory value assessed as unrelated to disease progression, intercurrent illness, or concomitant medications and occurring during the first course on study that meets any of the following criteria:

- CTCAE Grade 3 total bilirubin or AST (SGOT) or ALT (SGPT) for > 7 days
- CTCAE Grade 4 total bilirubin or AST (SGOT) or ALT (SGPT) of any duration

- All other clinically significant NCI common terminology criteria that are CTCAE Grade 3 or 4

An AE must be clinically significant to define DLT e.g. alopecia, study drug-related fever, electrolyte abnormalities (including K, Na, Cl, HCO₃, Mg, Ca) that are < Grade 3 will not define the DLT. Prolonged myelosuppression, as defined by the NCI criteria specific for leukemia, i.e. marrow cellularity <5% on day 42 or later from start of therapy without evidence of leukemia, will be considered as DLT. All other prolonged myelosuppressions will also be monitored closely. Note: As the patients receive 5-days of decitabine therapy prior to starting the induction chemotherapy, extra 5-days will be allowed to assess for prolonged myelosuppression. In addition to the above, patient death will be monitored closely. Any death will be submitted to discussion by the Department of Leukemia meeting.

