11. STATISTICAL CONSIDERATIONS

Phase I

First, phase I study is performed to assess the safety of different dosing schedules for clofarabine combined with fixed dosage of decitabine, idarubicin, and cytarabine. Two dose schedules are defined in table 1, and the starting dose schedule is dose level 1. A maximum of 18 AML patients will enroll in the phase I study.

Table 1: dose schedule

Dose level	Clofarabine 15 mg/m²/day IV daily
-1	Clofarabine daily for 3 days (days 6-8)
1	Clofarabine daily for 4 days (days 6-9)

Decitabine 20 mg/m² IV over approximately 1 hour daily for 5 days (days 1-5)

Idarubicin 10 mg/m² IV over approximately 30 minutes daily for 3 days (days 6-8)

Cytarabine 1 g/m² IV over approximately 2 hours daily for 5 days (days 6-10)

Dose Escalation Procedures

Starting with Dose level 1, the patient will be enrolled by cohort of 3. Once the DLT assessment for the 3 patients is completed, a sequential of another cohort of 3 patients will be enrolled. If at any time, we see more than 30% patients experiencing DLT, we will deescalate to dose level (-1). If no dose de-escalation occurs, with a total of 18 patients treated at dose level 1, dose level 1 will be considered as the MTD for the phase II part. If there is dose de-escalation, a cohort of 3 patients will be treated, Dose level -1 will be declared as MTD if there are ≤ 1 out of 6 patients experience DLT.

Phase II

Phase II part is a single arm study using the dosage schedule recommended from phase I. A maximum of 60 AML patients which includes 42 new patients and the 18 patients from phase I MTD level, and 20 ALL patients will be enrolled in the study. The trial will be continuously monitored regarding efficacy for each cohort, AML and ALL respectively. The toxicity will be jointly monitored for AML and ALL patients. The method of Thall, Simon, and Estey will be used to perform interim efficacy and safety monitoring.⁵³ The software Multc99.Version 2.1 was used to run the simulation.

Efficacy

The primary endpoint is the overall response which is defined as the best response (either CR, CRp, or CRi) within 56 days.

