11.2. ALL

For the ALL patients, the historical data suggested the overall response rate to current standard treatment is 20%. The target response rate would be 40% after the treatment. The trial will be continuously monitored. The study will be stopped early if the data suggest that:

$$\Pr(\pi > 0.2 | \text{data}) < 0.4$$

Here π is the overall response (OR) rate. That is, if at any time during the study we determine that there is a less than 40% chance that the average OR rate is greater than 20%, we will terminate the study. The OR rate is assumed to follow a non-informative prior of Beta (0.4, 1.6). The study will be stopped early if (The number of overall responses)/ (The number of patients evaluated) $\leq 1/8, 2/11, 3/17$.

Table 3: Operating characteristics for monitoring of overall response rate in ALL patients

True Response Rate	Early Stopping Probability	Median Sample size (interquartile)
0.15	0.85	8 (8,11)
0.2	0.7	11 (8, 20)
0.25	0.54	17 (8, 20)
0.3	0.38	20 (8,20)
0.35	0.26	20 (17, 20)
0.4	0.16	20 (20, 20)

Monitoring of non-hematological \geq grade 3 toxicities

With the concern of treatment related toxicity, the non-hematological toxicity (\geq grade 3) throughout all the cycles of treatment will also be closely monitored during the study for AML and ALL together.

Denote the probability of toxicity by P_E . We assume $P_E \sim \text{beta}(0.6, 1.4)$. Our stopping rule is given by the following probability statement: $\Pr(P_E > 0.3 \mid \text{data}) > 0.9$. That is, we will stop the trial if, at any time during the study, we determine that there is more than 90% chance that the toxicity rate is more than 30%. The study will be stopped early if (The number of non-hematological toxicities being grade 3 or higher)/ (The number of patients evaluated) $\geq 7/13, 8/15, 9/18, 10/21, 11/23, 12/26, 13/29, 14/32, 15/35, 16/38, 17/41, 18/43, 19/46, 20/49, 21/52, 22/55, 23/58, 24/61, 25/64, 26/67, 27/70, 28/73, 29/76, 30/79$. The operating characteristics are summarized in table 4.

Table 4: Operating characteristics for monitoring of non-hematological \geq grade 3 toxicities in AML or ALL patients

True Toxicity Rate	Early Stopping Probability	Median Sample size (interquartile)
0.25	0.15	80 (80, 80)
0.3	0.35	80 (27, 80)
0.35	0.63	42 (11, 80)
0.4	0.88	19 (7, 47)

Analysis method

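### One DLT in the first 3 at dose level -1 crosses Section 5.1's limit with no action stated, while Section 11 can still declare the MTD; separately, a drug-related death is not listed as a DLT

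*Combined protocol and SAP*

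**What the plan says.** **Dose rule.** Section 5.1 starts cohorts of 3 at dose level 1 and states: "If at any time, we see more than 30% patients experiencing DLT, we will de-escalate to dose level (-1"). It continues: "The same above monitoring rule will also be applied to dose level -1". The dose tables in Sections 5.2.1 and 11 contain only levels 1 and -1.

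Section 11 (Dose Escalation Procedures) repeats the 30% rule for level 1. For what follows de-escalation it says: "If there is dose de-escalation, a cohort of 3 patients will be treated, Dose level -1 will be declared as MTD" if no more than "1 out of 6 patients experience DLT". One cohort of 3 is mentioned, the criterion refers to 6 patients, and nothing connects the two. Neither section says what happens if level -1 fails.

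**DLT definition.** Section 5.2.1 lists hepatic criteria at Grade 3 (lasting more than 7 days) and Grade 4, then "All other clinically significant NCI common terminology criteria that are CTCAE Grade 3 or 4". Prolonged myelosuppression is added as a DLT. Death comes after the list: "In addition to the above, patient death will be monitored closely" and "Any death will be submitted to discussion by the Department of Leukemia meeting". No effect of a death on the DLT count or on the dose is stated. By contrast, the phase II toxicity stopping rule in Section 11 uses an open-ended grade: "The number of non-hematological toxicities being grade 3 or higher".

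**The concern.** The MTD is the phase I primary objective, and it fixes the number of clofarabine days for the phase II patients (up to 42 new AML and 20 ALL). Two gaps affect how it is reached.

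First, after 1 DLT in 3 at level -1 the investigator cannot tell whether to stop or to enrol 3 more. Section 5.1 says the limit has been crossed but offers only a move that has already been made. Section 11 implies that 6 patients may be treated. Whether level -1 becomes the MTD depends on which section is followed.

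Second, and independently, suppose the only event in the first cohort at level 1 is a drug-related death with no earlier countable Grade 3 or 4 event. Read literally, the cohort has 0/3 DLTs and 3 more patients enter at the same level. If the death counted, the result would be 1/3 and the dose would be reduced.

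**Working it through.** The plan gives no phase I operating characteristics and no expected DLT rate, so there is no figure to reproduce. I take true DLT rates p of 10%, 15%, 20% and 25% as assumptions and apply the limit after each completed cohort of 3.

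**Step 1: the two limits.** 1/3 = 33.3%, above 30%, so Section 5.1 is breached. 1/6 = 16.7%, so Section 11 accepts. The other route to 1/6 (0/3, then 1/3) never exceeds 30%. The sections therefore give opposite results on one path only: 1/3, then 0/3.

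**Step 2: how often level -1 opens.** With cohorts of 3 up to 18 patients, the limit at level 1 is crossed at 1/3, 2/6, 3/9, 4/12, 5/15 or 6/18. An exact binomial recursion over these boundaries gives the probability of de-escalation. Most of it comes from the first cohort: 1 − (1−p)³ is 0.271 at p = 10%, out of 0.300 in all.

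**Step 3: what happens at level -1.** With the same p at both levels:

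- Exactly 1 DLT in the first 3: 3p(1−p)². At 20%, 3 × 0.2 × 0.8² = 0.384.
- Conflicting path (1/3, then 0/3): 3p(1−p)⁵. At 20%, 3 × 0.2 × 0.8⁵ = 0.197.
- Level -1 accepted if 1/3 continues: (1−p)⁶ + 6p(1−p)⁵. At 20%, 0.262 + 0.393 = 0.655.
- Level -1 accepted if 1/3 stops: (1−p)³[(1−p)³ + 3p(1−p)²]. At 20%, 0.512 × (0.512 + 0.384) = 0.459.

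| True DLT rate | 10% | 15% | 20% | 25% |
|---|---|---|---|---|
| Level -1 opens | 0.300 | 0.447 | 0.588 | 0.713 |
| 1/3 at level -1, once open | 0.243 | 0.325 | 0.384 | 0.422 |
| 1/3 at level -1, overall | 0.073 | 0.145 | 0.226 | 0.301 |
| 1/3 then 0/3, once open | 0.177 | 0.200 | 0.197 | 0.178 |
| 1/3 then 0/3, overall | 0.053 | 0.089 | 0.116 | 0.127 |
| Level -1 accepted if 1/3 continues | 0.886 | 0.776 | 0.655 | 0.534 |
| Level -1 accepted if 1/3 stops | 0.709 | 0.577 | 0.459 | 0.356 |

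The overall rows are the once-open rows multiplied by the first row (at 20%, 0.588 × 0.197 = 0.116). The last two rows are conditional on level -1 being open, and they differ by exactly the conflicting path.

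**Step 4: unequal rates.** If level -1 has a rate of 5% to 25%, never above level 1, the overall probability of the conflicting path runs from 0.035 (level 1 at 10%, level -1 at 5%) to 0.142 (25% and 15%).

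**Step 5: death.** The boundaries in Step 2 show when one uncounted death matters: only when the counted DLTs are one short, for example 0/3, 1/6 or 2/9. The documents do not give the frequency. Section 2.3 reports 8% induction mortality with the CIA regimen, but does not attribute those deaths to drug, so it does not supply the rate.

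**The case against.** The two rules can be read together: Section 5.1 as a running limit and Section 11 as the final criterion. On that reading 1/3 at level -1 ends enrolment, level -1 is accepted only after 0/3 and then at most 1/3, and the conflicting path never arises. This is coherent, but it needs an instruction to stop at level -1 that appears nowhere. A conventional 3+3 reading, in which 1/3 leads to 3 more patients, fits Section 11's wording equally well.

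Neither reading selects a dose above level -1, and the 7% to 30% figure is the chance of reaching an undefined decision, not of choosing a wrong MTD. Both points are right and limit what the figures show. All of them also depend on assumed DLT rates.

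On death, a fatal toxicity first recorded at Grade 3 or 4 can count by that route, and every death goes to departmental discussion. That narrows the gap to deaths without an earlier countable event; it does not close it, because the discussion has no stated consequence for dose. The phase II rule covers fatal non-hematological toxicity, but its first listed boundary is 7/13 and it does not set the MTD.

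Finally, the cap of 18 phase I patients leaves no room for 6 at level -1 if level 1 is abandoned at patient 15 or 18 (15 + 6 = 21; 18 + 6 = 24). This is true, but it already follows from Section 11 as it stands. The probability is 0.1% to 2.0% over the assumed rates, and excluding those paths lowers the 12.7% at a 25% rate only to 12.3%.

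**Conclusion.** The concern holds, as two separate defects.

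At level -1 the protocol states two limits that give opposite verdicts on 1/3 then 0/3, and it states no action at the point where they part. With equal DLT rates of 10% to 25% at both levels, 5% to 13% of trials would take that path (3.5% to 14% if level -1 may be less toxic). The reading adopted changes the chance of accepting level -1, once it is open, by 18 to 20 percentage points. Level -1 is not a remote contingency: on the same assumptions it opens in 30% to 71% of trials.

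The DLT definition, followed literally, omits a course 1 drug-related death with no earlier countable event. Its frequency cannot be estimated from the documents, so this part rests on the text and on patient safety: such a death in the first cohort would leave the count at 0/3 and allow 3 more patients at the same dose.

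Both defects bear on the phase I primary objective and need correcting.

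**What to change.** 1. **Level -1 rule.** Put one rule in both Sections 5.1 and 11. For example: treat 3 patients at level -1; if at most 1 has a DLT, treat 3 more; level -1 is the MTD if at most 1 of 6 has a DLT; otherwise stop and do not open phase II. Delete the Section 5.1 sentence that carries the 30% rule to level -1, or limit it to match. If the sponsor prefers the stricter limit, state in both sections that 1 DLT in the first 3 ends enrolment at level -1. The consequence of failing at level -1 is the sponsor's decision, but it has to be written down. The same text should say whether the 18-patient cap may be exceeded to complete 6 at level -1 after a late de-escalation.

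2. **DLT definition.** In Section 5.2.1, extend the general criterion to Grade 3 or higher. Add that any course 1 death not attributed to disease progression, intercurrent illness or concomitant medication is a DLT.

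The cost is protocol wording in Sections 5.1, 5.2.1 and 11. No procedures are added, and no patients beyond the 6 that Section 11 already uses at level -1.
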